symptomatic and asymptomatic first and second trimester mothers will be included in the study and individually randomized to one of two arms: standard of care or enhanced cased detection arms using LAMP for malaria. Mothers will be enrolled during a twelve-months period from October 2020 to October 2021 and then followed until 28 days after delivery. Given the rate of pregnant mothers at the locations, we anticipate that the required minimum of 2583 mothers will be enrolled in the study during the study period. In the first standard of care arm, venous blood sample will be collected from each study participant and the presence of *Plasmodium* infection will be diagnosed by microscopy in symptomatic patients. Pregnant women who test positive for malaria will be referred and treated for malaria with quinine or ACTs as per national guidelines. In the second (test) arm, mothers whether symptomatic or asymptomatic will be tested by a commercially available CE-approved LAMP malaria test (Meridien Biosciences, Illumigene Malaria M kit, Cincinatti, USA) and Human Diagnostics LoopAMP (Wiesbaden, Germany) at each clinic visit in addition to RDT/microscopy. The commercial LAMP tests can distinguish P. falciparum and P. vivax and treatment will be given according to national guidelines. The purpose of doing all tests in the intervention arm is to determine how many additional cases LAMP identified. The primary outcome is the proportion of deliveries with low birth weight, with secondary outcomes of: (i) absolute birth weight; (ii) maternal hemoglobin; (ii) neonatal hemoglobin at birth (Standard Hgb testing from peripheral blood or finger prick); (iv) neonatal mortality; (v) stillbirth; and (vi) prematurity in each of the two arms. Additionally, signs of current or past *Plasmodium* sequestration in the placenta will be evaluated.

[figure not shown]

Figure 1: Flowchart summarizing randomized trial

There will be a total of at least five antenatal visits (mandatory). Emergencies (medical consultation outside the planned visit) will be recorded for each included woman. Visit 1 and 2 may be combined for mothers who present in the second trimester. The following table summarizes the procedures to be conducted at each visit.

Visit #	Time frame	Aim	Action for the study
1	Visit at health care center	Inclusion	Enrolment and randomisation
2	26 weeks gestation	Follow up	Malaria testing as per inclusion arm (2mL venous blood on EDTA) +ANC regular care Maternal Hgb

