5.3. Population

5.3.1. Study population

The study population will comprise pregnant women 18 years of age and above, in the first and second trimester, both symptomatic and asymptomatic, attending antenatal clinics during the study period. Gestational age will be determined using the mother's last normal menstrual period and by

measuring symphysis fundal height. Women will be assisted to determine their last normal menstruation with detailed calendar including local events reminder. Those who don't remember their last normal menstruation will not be included in the study. As described in the WHO guidelines, in high-transmission settings, where levels of acquired immunity tend to be high, *P. falciparum* infection is usually asymptomatic in pregnancy. Yet, parasites may be present in the placenta and contribute to maternal anemia even in the absence of documented peripheral parasitemia. Both maternal anemia and placental parasitemia can lead to low birth weight, which is an important contributor to infant mortality. In high-transmission settings, the adverse effects of *P. falciparum* infection in pregnancy are most pronounced for women in their first pregnancy. In low-transmission settings women of reproductive age have relatively little acquired immunity to malaria, malaria in pregnancy is associated with anemia, an increased risk of severe malaria, and it may lead to spontaneous abortion, stillbirth, prematurity and low birth weight. We hypothesize that both symptomatic and asymptomatic cases of malaria occur in pregnant women. Patients who are positive by LAMP and negative by microscopy will be consented for treatment based on the evidence that LAMP has greater sensitivity.

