For any adverse event, women will be given the contact of the local study coordinator. Community Health Worker will be sensitive to the study. At the following ANC visit, women will be encouraged to report any side effect or concern to the study staff. Each local study site coordinator will summarize any adverse event on a monthly basis and transmit the corresponding information to the national coordinator. Proper pharmacovigilance notification will be operated to the health authorities if necessary.

The LAMPREG clinical trial aims to evaluate the impact of active detection of both sub microscopic symptomatic MiP and asymptomatic (microscopic and submicroscopic) MiP. In this trial, even asymptomatic and submicroscopic MiP will be treated for *Plasmodium* spp infection as if they were uncomplicated MiP cases. The proposed used drugs fall under the drugs approved by Ethiopia Food, Medicine and Health Care Administration and Control Authority and have been proven safe during pregnancy. Importantly, the benefits of the treatment overpass the risk due to treatment induction. Information sheet and informed consent were modified to provide information regarding the treatment risk. Importantly, drugs prescription will be at the discretion of the physician assessing the women, and women safety will be the main priority of the medical staff in charge of the study.

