data collection", "lost to follow up". This will be presented in CONSORT diagram format rather than as a table, with numbers and reasons for withdrawal and/or exclusion from the analysis given at each stage. The numbers (with reasons) of losses to follow-up (dropouts and withdrawals) over the course of the trial will be summarized by treatment arm.

5. Population and subgroup to be analyzed

Intention-to-treat (ITT): All randomized study subjects. This will be the primary population for the analysis.

Per Protocol (PP): All randomized study subjects completing the whole study period (complete cases). For a specific analysis, study subjects with missing data on any of the variables in the model will be excluded from the analysis. Analyses of this population is seen as a sensitivity analysis to investigate whether conclusions are sensitive to assumptions regarding the pattern of missing data

We will analyze independently the following subgroups (Both ITT and PP populations):

- a. Primiparous mother
- b. **Asymptomatic malaria**: women who did not present symptom at any ANC visit but were detected positive for *Plasmodium* spp infection by any diagnostic method.
- c. **Sub microscopic malaria**: any women diagnosed positive for malaria by molecular method (LAMP or post hoc gold standard RT-qPCR)
- d. Malaria species identified: *P. falciparum*, *P. vivax* and mixed infections (3 subgroups)
- e. Women presenting positive malaria testing in placental blood at delivery
- f. Women from newborn with Low Birth Weight

6. Baseline patient characteristics

Expectant women will be described with respect to age, parity, gestity, gestational age, history of malaria, pregnancy complication, both overall and separately for the two randomized groups. These data will be summarized in a table.

Section 6: Analysis

1. Outcome definition

Primary study outcomes are related to newborn health: fetal anemia (hemoglobin <12.5 g/dL), mean birthweight, low birthweight (<2500 g), mean gestational age, preterm delivery (<37 weeks' gestation), mean birthweight for gestational age (Z scores), small for gestational age, fetal loss (spontaneous abortion at <28 weeks' gestation or stillbirth), and the composite outcomes of adverse livebirth (preterm, low

birthweight, or small for gestational age) and adverse pregnancy (adverse livebirth or fetal loss). Mortality outcomes included neonatal, perinatal, and mortality up to age 4 weeks.

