Secondary outcomes were signs of placental malaria infection at delivery, defined as a composite of maternal malaria (detection of infection in peripheral blood with post hoc gold standard testing) or placental malaria (detection of infection in placental blood with microscopy, molecular testing for active infection, or malaria pigment in blood smear monocytes for signs of past infection)

Secondary outcomes include maternal anemia (any: hemoglobin level <11 g/dL; moderate: hemoglobin level <9 g/dL) during each ANC visit and at delivery. We will use the categories "no anemia", "mild anemia", "moderate anemia" and "severe anemia" using the reference values for each pregnancy trimester. Values will be disaggregated according to gestational age.

Secondary outcomes during pregnancy comprised maternal malaria, detected with any method and by each method separately. This outcome was further stratified by patent infection (positive microscopy or malaria rapid diagnostic test) and sub-patent infection (negative microscopy and malaria rapid diagnostic test and positive LAMP–PCR). Morbidity outcomes assessed during pregnancy comprised clinical malaria (documented or history of fever plus positive malaria rapid diagnostic test or microscopy) and unscheduled clinic visits for any reason and for all reasons unrelated to malaria.

2. Analysis methods

Mean values of quantitative variables will be compared using a two-sided t-test with a significance of p < 0.05. We will use a negative binomial model to assess the effect of asymptomatic malaria screening using the number of (i) both microscopic and submicroscopic and (ii) submicroscopic *P. falciparum* infections occurring during pregnancy with an adjustment for the confounding variables. Multiple test correction will be implemented.

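### The SAP's sub microscopic malaria subgroup admits every molecular-positive woman, so it mixes in microscopic infections and conflicts with the SAP's own sub-patent rule

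*SAP*

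**What the plan says.** SAP Section 5, item 5 lists subgroups to be analysed in both the ITT and per-protocol populations. Subgroup c, labelled sub microscopic malaria, is "any women diagnosed positive for malaria by molecular method (LAMP or post hoc gold standard RT-qPCR". It sets no condition on microscopy or RDT.

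SAP Section 6 uses two related ideas:

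- Item 1 (outcome definition) splits maternal malaria into patent and sub-patent infection. Sub-patent requires "negative microscopy and malaria rapid diagnostic test and positive LAMP" or PCR.
- Item 2 (analysis methods) plans a negative binomial model on the number of *P. falciparum* infections in pregnancy, counted as "i) both microscopic and submicroscopic and (ii) submicroscopic" alone.

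The protocol also keeps the categories apart. Section 5.12 says the trial "aims to evaluate the impact of active detection of both sub microscopic symptomatic MiP and asymptomatic (microscopic and submicroscopic) MiP". Section 5.3.1 describes the additional cases as LAMP positive and film negative: "Patients who are positive by LAMP and negative by microscopy will be consented for treatment". Section 5.2 explains the parallel testing: "The purpose of doing all tests in the intervention arm is to determine how many additional cases LAMP identified".

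**The concern.** LAMP and RT-qPCR detect most infections that microscopy detects, as well as those it misses. A group defined only by a positive molecular test is therefore all molecular-positive women, and the label sub microscopic does not describe it.

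The label matters because LAMP's claimed added value lies in infections that a film would miss. A result reported for this subgroup would be read as evidence on low-density infection, while part of it came from women a film would have identified.

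The error could also spread. Subgroup c is the only place where the SAP defines the word submicroscopic; Section 6 attaches the stricter rule to a different word, sub-patent. An analyst who carried the subgroup c definition into the negative binomial model would make count (ii) nearly the same as count (i), and the planned contrast would largely disappear.

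**Working it through.** **Definitions side by side**

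| Place | Term | Molecular test | Microscopy | RDT |
|---|---|---|---|---|
| SAP 5, item 5(c) | sub microscopic | positive | no condition | no condition |
| SAP 6, item 1 | sub-patent | positive | negative | negative |
| SAP 6, item 2, count (ii) | submicroscopic | not stated | contrasted with microscopic | not stated |
| Protocol 5.3.1 | additional LAMP cases | LAMP positive | negative | not stated |

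Only subgroup c lets a film-positive woman in.

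**Reproducing the plan's figure.** The SAP gives no expected size for this subgroup. The nearest stated figure is microscopy sensitivity in the phase 2 pilot (protocol Section 3, Table 3): 25.0% (5.49–57.19). An exact (Clopper-Pearson) interval for 3/12 gives 25.0% (5.49–57.19), so the figure is reproduced.

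**Share of the subgroup that is microscopic.** Let M be the film-positive infected women, R the reference-positive women, and F the LAMP-positive, reference-negative women. Subgroup c takes LAMP *or* RT-qPCR positives, so F also enters. The share is M/R if F is ignored and M/(R + F) if it is counted. Both forms assume that all M women are molecular positive and all R women enter.

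*Phase 2 pilot (34 women, 28 asymptomatic):*
- M = 3, R = 12.
- Commercial LAMP specificity of 86.96% is 20/23, so F = 3.
- Ignoring F: 3/12 = 25%.
- Counting F: 3/(12 + 3) = 3/15 = 20%.
- The commercial LAMP row implies 11 reference positives (81.82% = 9/11), while the microscopy row implies 12. If the twelfth woman is one of the three LAMP false positives, the share is 3/14 = 21%. The range is unchanged.

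*Phase 1 pilot (87 symptomatic women; Tables 1 and 2):*
- R = 3 + 5 + 1 + 1 = 10 PCR positives; 87 − 10 = 77 negatives.
- Microscopy sensitivity 90%: M = 0.90 × 10 = 9.
- LAMP specificity 93.5%: F = 0.065 × 77 ≈ 5.
- Ignoring F: 9/10 = 90% (exact 95% interval 55.5–99.7%; Table 2 prints 66.3–100).
- Counting F: 9/(10 + 5) = 9/15 = 60%.

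**What the subgroup would estimate.** If a share w of the group is microscopic, an effect averaged over it is approximately (1 − w) × submicroscopic effect + w × microscopic effect:
- w = 0.25: 0.75 × submicroscopic + 0.25 × microscopic
- w = 0.60: 0.40 × submicroscopic + 0.60 × microscopic
- w = 0.90: 0.10 × submicroscopic + 0.90 × microscopic

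The documents give neither effect, so the direction and size of the distortion cannot be calculated.

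**The case against.** A reader might infer that the trial cannot address submicroscopic infection at all. The documents do not support that. The sub-patent stratification and the separate submicroscopic count in SAP Section 6 both remain. The protocol statement on submicroscopic infection is in the ethics section; it is not a numbered objective in Section 4.2, and it does not promise a submicroscopic-only effect.

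A reader might also take 25–90% as the microscopic share. That treats microscopy sensitivity as if it were the share of the subgroup, and omits LAMP-positive, reference-negative women. The 90% figure further needs a wholly symptomatic group, whereas 28 of 34 women in the antenatal pilot were asymptomatic.

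Nor do the documents show that the conclusion on low-density infection would be wrong. They show a mixture under a misleading label, in one of several subgroups with no confirmatory claim attached.

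Finally, sub-patent and submicroscopic are not identical. A film-negative, RDT-positive woman is submicroscopic but patent, so copying the sub-patent rule into subgroup c would change the concept slightly.

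These points limit the scope and size of the concern and shape the remedy. They do not remove the inconsistency: nothing in either document restricts subgroup c to film-negative women.

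**Conclusion.** Subgroup c is wrong for its label and inconsistent with SAP Section 6. Followed as written, it reports microscopic and submicroscopic infections together as submicroscopic. It should be corrected before analysis, but the randomised low birth weight comparison and the sample size do not depend on it.

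On the pilots, the microscopic share might be about 20–25% in mostly asymptomatic women and 60–90% in symptomatic women. This assumes that pilot test performance carries over to the trial, and it rests on 3/12 and 9/10 infections, so it shows only that the overlap need not be trivial.

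The SAP cites protocol version 1.5, and the protocol reviewed is version 1.1. The conflict between SAP Sections 5 and 6 does not depend on that difference.

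**What to change.** 1. Define a submicroscopic *sample* as molecular positive with negative microscopy on the same sample. Keep the term sub-patent for samples where the RDT is also negative.
2. Classify a *woman* as submicroscopic only if she has at least one such sample and no microscopy-positive sample during pregnancy. For sub-patent, also require no RDT-positive sample.
3. Report women with any microscopic infection as a separate group.
4. Label molecular-positive samples with no film read as microscopy not done, and do not count them as submicroscopic.
5. Use the same submicroscopic definition for count (ii) of the negative binomial model.

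The change is to SAP wording, but it has two costs. The subgroup becomes smaller and its intervals wider. The film condition may also act unequally by arm. Protocol 5.2 states microscopic diagnosis in standard of care only for symptomatic women, while 5.7.2 describes films from each participant and dried blood spots from all. If asymptomatic standard-of-care films are not read, the microscopy-not-done label could remove asymptomatic women from that arm only. The SAP should state which films are read. Unless they are read on the same basis in both arms, report the subgroup descriptively and not as a between-arm effect. Even with equal reading, membership depends on post-randomisation test results, which is a separate limit on any between-arm reading.

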5.7.2. Blood sample collection and processing

For microscopy, two milliliters of venous blood will be collected from each study participant using EDTA anticoagulant test tube. Soon after venous blood collection, a drop of blood will be taken for RDT test and another two separate drops of blood will be placed on frosted microscope slides to prepare thin and thick blood films. For LAMP, two milliliters of venous blood will be collected from each study participant using EDTA anticoagulant test tube. LAMP will be performed at the respective health centers based on the manufacturer's recommendation (Meridian Diagnostics, and Human Diagnostics). Dried blood spot (DBS) samples will also be collected from all individuals by using two drops of blood placed on a Whatmann filter paper. DBS will be stored in AHRI for further testing if required. DBS will also be sent to the University of Calgary, Canada (cf MTA) for ultrasensitive malaria technique (qRT PCR) and parasitic whole genome sequencing. For placental infection assessment, placental blood will be collected on anticoagulant after delivery.

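### Malaria status is ascertained differently in the two arms: a positive LAMP alone makes a case, but only the intervention arm is tested by LAMP

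*SAP*

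**What the plan says.** **Who counts as a case.** SAP Section 5.5 introduces its subgroups with "We will analyze independently the following subgroups (Both ITT and PP populations". Subgroup (b) is "women who did not present symptom at any ANC visit but were detected positive for" *Plasmodium* on whichever test was used. Subgroup (c) is "any women diagnosed positive for malaria by molecular method (LAMP or post hoc gold standard RT-qPCR"; despite its name, it does not ask for negative microscopy. SAP 6.1 takes maternal malaria during pregnancy as "detected with any method and by each method separately". Its sub-patent stratum needs microscopy and RDT both negative and a molecular test positive. SAP 6.2 plans a "negative binomial model to assess the effect of asymptomatic malaria screening", based on the number of infections in pregnancy.

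**Who is tested.** In the standard arm, Protocol 5.2 says "infection will be diagnosed by microscopy in symptomatic patients". In the intervention arm every woman has LAMP plus microscopy/RDT at each visit, and "The purpose of doing all tests in the intervention arm is to determine how many additional cases LAMP identified". Protocol Table 5 makes testing at visits 2 to 4 depend on the arm, and SAP 3.1 speaks of LAMP being added to one arm.

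**What both arms share.** Protocol 5.7.2 states "Dried blood spot (DBS) samples will also be collected from all individuals" and sends the spots for qRT-PCR. The same section says that blood for LAMP is drawn from every participant, but no text says that LAMP is run in the standard arm.

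**The concern.** An intervention-arm woman has two molecular routes into subgroup (c), and a standard-arm woman has one. Membership therefore depends on the arm as well as on infection, even though the rule is worded once for everyone.

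Two kinds of result are exposed. The first is any between-arm count of malaria: subgroups (b) and (c), maternal malaria by any method, and the negative binomial model if it compares arms. Such counts would mix better detection with positives that the reference test does not confirm. The second is any birth outcome compared between arms inside (b) or (c). If the unconfirmed women are mostly uninfected and at lower risk, adding them to one arm only lowers that arm's proportion with low birth weight, whether or not treatment works.

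Sub-patent infection has a further imbalance. It needs negative microscopy and RDT, which the design text does not plan for asymptomatic standard-arm women.

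**Working it through.** **The plan's own figure.** With 17.3% against 12.3%, two-sided alpha 0.05, 80% power, 3:1 allocation and continuity correction, the standard arm needs 538 women and the trial 538 × 4 = 2152. Then 2152 × 1.2 = 2582.4, rounded up to 2583. Malaria status does not enter this calculation.

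**Pilot inputs (Protocol Section 3).**
- Table 2: 87 women, 10 PCR-positive. LAMP sensitivity 100% = 10/10; specificity 93.5% = 72/77. So 15 are LAMP-positive and 5 of them PCR-negative.
- Table 3, Meridian kit: 81.82% = 9/11 and 86.96% = 20/23. So 12 are LAMP-positive and 3 of them reference-negative. The 11 reference positives match the qPCR count of 11/34.

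**Share counted as positive**, assuming equal infection in both arms and one testing round:

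| | LAMP arm (LAMP or PCR) | Standard arm (PCR) | Ratio |
|---|---|---|---|
| Table 2 | 15/87 = 17.2% | 10/87 = 11.5% | 1.50 |
| Table 3 | (11 + 3)/34 = 41.2% | 11/34 = 32.4% | 1.27 |

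**PCR-negative share *s* of subgroup (c) in the LAMP arm.** Table 2: 5/15 = 33% (exact 95% CI 12 to 62). Table 3: 3/14 = 21% (5 to 51). In the standard arm it is 0.

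**False difference in low birth weight within (c)**, if treatment does nothing. Let *p* be the prevalence (10/87 or 11/34) and *R* the assumed risk ratio for infected against uninfected women. Hold overall risk at the design's 17.3% and give unconfirmed women the uninfected risk:
- r0 = 17.3% / (1 + p(R − 1)), and r1 = R × r0.
- The standard arm in (c) has risk r1. The LAMP arm has (1 − s)r1 + s·r0.
- The difference is s(r1 − r0).

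For R = 2 at Table 2 rates, r0 = 17.3/1.115 = 15.5% and r1 = 31.0%, so the difference is 15.5/3 = 5.2 points.

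| R (assumed) | Table 2 rates | Table 3 rates |
|---|---|---|
| 1.25 | 1.4 points | 0.9 points |
| 1.5 | 2.7 points | 1.6 points |
| 2 | 5.2 points | 2.8 points |

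**Unconfirmed LAMP-positive women per testing round**, before attrition. SAP 3.2 gives 2:1 allocation and SAP 3.3 gives 3:1, so both are shown:
- 2:1: 2583 × 2/3 = 1722; × 5/87 = 99, × 3/34 = 152.
- 3:1: 2583 × 3/4 = 1937; × 5/87 = 111, × 3/34 = 171.

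**The case against.** **The false benefit needs an analysis that the SAP does not spell out.** SAP 5.5 says only that subgroups are analysed independently. Subgroup (f), mothers of low-birth-weight newborns, could not support a between-arm comparison of low birth weight. SAP 6.2 relates birth outcomes to malaria status rather than to arm, and Protocol 5.8 mentions LAMP and microscopy positivity within the intervention arm. This stands: the 0.9 to 5.2 points are conditional. Still, a superiority trial analysing subgroups of its ITT and PP populations implies a comparison of arms, and the imbalance in malaria counts does not need this step.

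**Part of the remedy is already planned.** Maternal malaria is also to be reported for each method, so a qRT-PCR result will exist. LAMP predictive values against PCR, together with counts of LAMP positives, would show unconfirmed positives at test level. This also stands, so a reader should not infer that they would be hidden. It does not change who enters (b) or (c).

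**LAMP might be run in both arms.** The blood-collection sentence in Protocol 5.7.2 could be read so. It describes a sample, not a test. Because Protocol 5.7.4 has LAMP positives treated, testing the standard arm in real time would remove the contrast between arms. The protocol at hand is v1.1, while the SAP is written to v1.5, which may be clearer.

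**The pilot evidence is thin.** The estimates rest on 5 and 3 women. Table 2 was retrospective and symptomatic, and its printed specificity interval reaches 100%. A negative qRT-PCR does not exclude infection: in Table 3 qPCR missed 1 of 12 consensus positives, so by consensus 2 or 3 of the 12 Meridian positives were negative. All of this stands as a limit on size, not on the asymmetry.

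**Conclusion.** The point holds as one of unequal ascertainment. Followed exactly, the SAP lets LAMP-positive, qRT-PCR-negative women into subgroups (b) and (c) and into any-method maternal malaria from the intervention arm only. At pilot rates, equal infection and one round, this inflates apparent malaria in that arm by a ratio of 1.27 to 1.50. The bias in low birth weight within (c) is about 0.9 to 5.2 points under the assumed risk ratios and a between-arm comparison. It is zero if unconfirmed women carry the same risk as confirmed women, and near zero if LAMP is almost perfectly specific.

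Four stronger readings are not supported:
- *The definition differs by arm.* It is written once; only the tests that feed it differ.
- *The main result is biased.* The primary ITT low-birth-weight comparison and N = 2583 do not use malaria status. The delivery composite in SAP 6.1 takes peripheral infection from post hoc gold standard testing and is neutral between arms as written.
- *The distortion rivals the trial's 5-point target.* That target is for the whole randomised population, not for a subgroup. Nor can the literature review's 19% of low birth weight attributed to malaria be combined with Table 2 prevalence to claim more: it would imply r0 = 0.81 × 17.3 = 14.0%, R = 1 + (0.19/0.81)/(10/87) = 3.04, and a low-birth-weight risk of 3.04 × 14.0 = 42.6% in infected women, which is implausible.
- *Repeated visits must multiply the gap.* At Table 2 rates the ratio would reach 2.8 over four rounds if false positives were independent, but the documents do not show that. If the same women recur, it stays nearer 1.5.

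**What to change.** - For every between-arm use of malaria status (SAP 5.5(b), 5.5(c), maternal malaria in 6.1, infection counts in 6.2), define infection by qRT-PCR on dried blood spots at visits sampled in both arms. Prefer the first sampled visit, because later infection is altered by treatment given after randomisation.
- Report LAMP-based and sub-patent detection within the intervention arm only. Split LAMP's additional cases into qRT-PCR confirmed and unconfirmed, and keep the unconfirmed in the total.
- State which outcomes are compared between arms within each subgroup.

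The cost is SAP wording and a split of counts from testing already planned. There are two downsides. These results must wait for the post-trial qRT-PCR: SAP 3.6 puts the clinical analysis in the second half of 2022 and laboratory results between the end of 2022 and the first half of 2023, and SAP 3.5 notes that reference testing will be missing at the second interim. They are also limited to visits with a stored blood spot. Protocol Table 5 does not list blood spots, so the visits at which they are taken should be confirmed first.
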